**14.3.2 Listing of Deaths, Other Serious and Significant Adverse Events****Table 61: Listing of Serious Adverse Events**

Maternal/Infant	Adverse Event	Estimated Gestational Age/Infant Age	No. of Days Post Dose (Duration)	No. of Days Post Dose the Event Became Serious	Reason Reported as an SAE	Severity	Relationship to Study Treatment	If Not Related, Alternative Etiology	Subject Discontinued Due to AE	Outcome	MedDRA System Organ Class	MedDRA Preferred Term
Subject ID: , Treatment Group: , AE Number:												
Comments:												
Subject ID: , Treatment Group: , AE Number:												
Comments:												

**Table 62: Listing of Major Congenital Anomalies**

Maternal/Infant	Adverse Event	Estimated Gestational Age/Infant Age	No. of Days Post Dose (Duration)	No. of Days Post Dose the Event Became Serious	Reason Reported as an SAE	Severity	Relationship to Study Treatment	If Not Related, Alternative Etiology	Subject Discontinued Due to AE	Outcome	MedDRA System Organ Class	MedDRA Preferred Term
Subject ID: Treatment Group: , AE Number:												
Comments:												
Subject ID: Treatment Group: , AE Number:												
Comments:												

**Table 63: Listing of Non-Serious, Unsolicited, Moderate or Severe Adverse Events**

Maternal/Infant	Adverse Event	Estimated Gestational Age/Infant Age	No. of Days Post Associated Dose (Duration)	Severity	Relationship to Study Treatment	If Not Related, Alternative Etiology	Subject Discontinued Due to AE	Outcome	MedDRA System Organ Class	MedDRA Preferred Term
Subject ID: , Treatment Group: , AE Number:										
Comments:										
Subject ID: , Treatment Group: , AE Number:										
Comments:										

**Table 64: Listing of New Onset Chronic Medical Conditions**

Maternal/Infant	Adverse Event	Estimated Gestational Age/ Infant Age	No. of Days Post Dose	Duration of Event	Severity	MedDRA System Organ Class	MedDRA Preferred Term	Relationship	Outcome
Subject ID: , Treatment Group: , AE Number:									
Comments:									
Subject ID: , Treatment Group: , AE Number:									
Comments:									

### **14.3.3 Narratives of Deaths, Other Serious and Significant Adverse Events**

(not included in SAP, but this is a placeholder for the CSR)

#### **14.3.4 Abnormal Laboratory Value Listings (by Subject)**

Not Applicable.

### **14.3.5 Displays of Laboratory Results**

#### **14.3.5.1 Chemistry Results**

Not Applicable.

#### **14.3.5.2        Hematology Results**

Not Applicable.

#### **14.3.5.3 Urinalysis Results**

Not Applicable.

#### 14.3.6 Displays of Vital Signs

**Table 65: Vital Signs in Maternal Subjects by Maximum Severity, Time Point, and Treatment Group – Any Assessment**

Time Point	Treatment Group	N	None		Mild		Moderate		Severe		Missing	
			n	%	n	%	n	%	n	%	n	%
Baseline	BOOSTRIX	x	x	xx	x	xx	x	xx	x	xx	x	xx
	Td											
Day 31	BOOSTRIX											
	Td											
Delivery	BOOSTRIX											
	Td											
Max Severity Post Baseline	BOOSTRIX											
	Td											

Note: The “Max Post Baseline” rows indicate the maximum severity experienced by each subject at any time point post baseline, including unscheduled assessments.

N = Number of subjects in the Maternal Safety Population

Tables with similar format:

**Table 66: Vital Signs in Maternal Subjects by Maximum Severity, Time Point, and Treatment Group –Oral Temperature**

**Table 67: Vital Signs in Maternal Subjects by Maximum Severity, Time Point, and Treatment Group –Pulse**

**Table 68: Vital Signs in Maternal Subjects by Maximum Severity, Time Point, and Treatment Group –Blood Pressure**

**Table 69: Vital Signs in Infant Subjects by Maximum Severity and Treatment Group – Any Assessment**

Time Point	Treatment Group	N	None		Mild		Moderate		Severe		Missing	
			n	%	n	%	n	%	n	%	n	%
Birth	BOOSTRIX	x	xx	xx	x	xx	xx	x	xx	xx	x	xx
	Td											

N = Number of subjects in the Infant Safety Population

Tables with similar format:

**Table 70: Vital Signs in Infant Subjects by Maximum Severity and Treatment Group – Axillary Temperature****Table 71: Vital Signs in Infant Subjects by Maximum Severity and Treatment Group – Heart Rate****Table 72: Vital Signs in Infant Subjects by Maximum Severity and Treatment Group – Respiratory Rate**

## 14.4 Summary of Concomitant Medications

**Table 73: Number and Percentage of Subjects with Prior and Concurrent Medications by WHO Drug Classification and Treatment Group – Maternal Subjects**

WHO Drug Code Level 1, Anatomic Group	WHO Drug Code Level 2, Therapeutic Subgroup	BOOSTRIX (N=X)		Td (N=X)		All Subjects (N=X)	
		n	%	n	%	n	%
Any Level 1 Codes	Any Level 2 Codes	x	xx	x	xx	x	xx
[ATC Level 1 – 1]	Any [ATC 1 – 1]						
	[ATC 2 – 1]						
	[ATC 2 – 2]						
	[ATC 2 – 3]						
[ATC Level 1 – 2]	Any [ATC 1 – 2]–						
	[ATC 2 – 1]						
	[ATC 2 – 2]						

N = Number of subjects in the Maternal Safety Population.

n=Number of subjects reporting taking at least one medication in the specific WHO Drug Class.

**Table 74: Number and Percentage of Subjects with Prior and Concurrent Medications by WHO Drug Classification and Treatment Group – Infant Subjects**

WHO Drug Code Level 1, Anatomic Group	WHO Drug Code Level 2, Therapeutic Subgroup	BOOSTRIX (N=X)		Td (N=X)		All Subjects (N=X)	
		n	%	n	%	n	%
Any Level 1 Codes	Any Level 2 Codes	x	xx	x	xx	x	xx
[ATC Level 1 – 1]	Any [ATC 1 – 1]						
	[ATC 2 – 1]						
	[ATC 2 – 2]						
	[ATC 2 – 3]						
[ATC Level 1 – 2]	Any [ATC 1 – 2]–						
	[ATC 2 – 1]						
	[ATC 2 – 2]						

N = Number of subjects in the Infant Safety Population.

n=Number of subjects reporting taking at least one medication in the specific WHO Drug Class.

## 14.5 Pregnancy Reports

**Table 75: Summary of Pregnancy Outcomes by Treatment Group**

Pregnancy Outcome	BOOSTRIX (N=X)			Td (N=X)			All Subjects (N=X)		
	n	%	95% CI	n	%	95% CI	n	%	95% CI
Live Births	x	xx	x.x, x.x	x	xx	x.x, x.x	x	xx	x.x, x.x
Spontaneous Abortions									
Elective Abortions or Still Births									

Note: N= Number of subjects in the Maternal Safety Population

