## 5. SAMPLE SIZE CONSIDERATIONS

Based on the accrual rate for similar studies, it seems reasonable to expect that the sites will be able to enroll this study in a timely fashion. Prior experience suggests up to 15% of subjects may be excluded from the per protocol analysis for the primary immunogenicity outcome either because they were lost-to-follow-up or otherwise do not have data available following the study vaccination, or because they had a protocol deviation requiring their exclusion from the per protocol analysis.

The study is planned to enroll 200 pregnant women (133 BOOSTRIX, 67 Td) and their infants.

This will be one of the first studies of maternal Tdap vaccination in an African, low resource setting, and where infants received whole cell, rather than acellular pertussis vaccinations. Thus, this study is intended to obtain preliminary estimates of immune response in this setting; it is not designed to test a specific null hypothesis.

**Table 3** indicates the probability of observing one or more safety event, such as solicited injection site or systemic symptom, or an unsolicited adverse event of a particular type within a treatment arm.

In addition to safety, as a co-primary objective, the study will assess serum PT antibody at birth among infants whose mothers received a single dose of BOOSTRIX or Td, and as secondary and exploratory objectives, the study will assess maternal and infant humoral response to all vaccine antigens. Immune response will be measured by ELISA. **Table 4** presents the precision (95% confidence interval (CI)) available for estimating GMC of ELISA titers against the vaccine component using assumptions for GMC and standard deviation (SD) for maternal and infant response to Tdap from Munoz et al. [10] and infant response post third dose of primary DTwP vaccine series from Ladhani et al. [11]

**Table 5** presents the minimum difference in infant PT antibody GMC at birth between the Td and Tdap (BOOSTRIX) vaccination arms that would be detectable with 80% power. The assumed GMC and SD used for these calculations are based on the PT antibody GMC and SD observed at birth in infants whose mother received either Tdap or placebo vaccination during pregnancy, reported in Munoz et al. [10] The calculations are based on a two-sided two sample T-test to compare means, with alpha = 0.05.

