#### **9.5. Pregnancies**

Every attempt was made to follow subjects to completion of pregnancy to document the outcome, including information regarding any complications with pregnancy and/or delivery. A table summarizing the total pregnancies, number of live births, and number of spontaneous abortions, elective abortions or still births by treatment group will be presented ([Table 75](#)). In addition, a listing of pregnancies and outcomes will be presented ([Listing 18](#), [Listing 19](#), [Listing 20](#), and [Listing 21](#)). A summary of infant size for gestational age at birth by treatment group will be presented in [Table 76](#) and [Figure 233](#).

Pregnancy related adverse events will be collected throughout the study and graded on a scale of 0 (absent), 1 (mild), 2 (moderate) and 3 (severe). Pregnancy related maternal events include pregnancy loss, bleeding during pregnancy or labor, postpartum hemorrhage, postabortal endometritis/salpingitis, preterm rupture of membranes, preterm contractions/labor/delivery, poor fetal growth, hypertension/preeclampsia/eclampsia, chorioamnionitis, postpartum endometritis, gestational diabetes and other pregnancy related AE. Infant events include preterm birth, birth weight, neonatal complications in a term infant, other AE in newborn and congenital abnormality/birth defect ([Table 8](#)).

The proportion of subjects reporting at least one pregnancy related adverse event will be summarized for each pregnancy related adverse event, any maternal symptom, and any infant symptom. The 95% CI will be calculated using Clopper-Pearson methodology from a binomial distribution (SAS Proc Freq with a binomial

(exact) option) will be presented ([Table 77](#) and [Table 78](#)). A Fisher's exact test w the difference in the proportion of subjects reporting a pregnancy related adverse event ([Table 79](#) and [Table 80](#)).

For each pregnancy related event, any maternal event, and any infant event, the maximum severity will be summarized for the maternal and infant Safety populations. The number and percentage of subjects reporting each event will be summarized by the maximum severity and treatment group. ([Table 81](#) and [Table 82](#)). The frequency of pregnancy- and infancy-related adverse events are presented in a bar chart in [Figure 229](#) and [Figure 231](#). The incidence of pregnancy- and infancy-related AEs are presented in [Figure 230](#) and [Figure 232](#).

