Table 8: Solicited Adverse Event Grading Scale (continued)

	Mild (Grade 1)	Moderate (Grade 2)	Severe (Grade 3)
Allergic Reaction	Pruritus without rash	Localized urticaria OR requires oral therapy	Generalized urticaria; angioedema OR anaphylaxis OR requires epinephrine
Systemic (Quantitative)			
Fever % - oral #†	38.0 – 38.4°C 100.4 – 101.1°F	38.5 – 38.9°C 101.2 – 102.0°F	> 38.9°C ≥ 102.1°F
Bradycardia - beats per minute	50 – 54 or 45-50 if baseline <60 bpm	45 – 49 or 40-44 if baseline <60 bpm	< 45 or <40 if baseline <60 bpm
Tachycardia - beats per minute	101 – 115	116 – 130	> 130 or ventricular dysrhythmias
Hypotension (systolic) mm Hg	85-89	80-84	< 80
Hypertension (systolic) mm Hg	141-150	151-160	> 160
Hypertension (diastolic) mm Hg	91-95	96-109	> 109
Maternal Adverse Events (Adverse Events During Pregnancy)			
Pregnancy loss b (Pregnancy does not result in a live birth)  Spontaneous abortion or miscarriage in the first or second trimester of gestation  Fetal death at or after 20 weeks of gestation (stillbirth)	N/A	N/A	Spontaneous abortion or miscarriage
Bleeding (vaginal) during pregnancy prior to the onset of labor	Spotting or bleeding less than menses	Bleeding like menses or heavier, no intervention indicated	Profuse bleeding with dizziness or orthostatic hypotension, transfusion indicated
Postpartum hemorrhage	EBL c 501-1000 for vaginal delivery or 1001-1500 for CS or reported as slightly increased	EBL >1000 for vaginal delivery or >1500 for CS, with or without mild dizziness, no transfusion required	Hemorrhage at a level for which transfusion of packed cells or any amount of other blood components is indicated
Postabortal endometritis/salpingitis	Low grade fever and uterine tenderness, resolved with oral antibiotics	Moderate symptoms, requiring ≤3 days of parenteral antibiotics	Severe symptoms requiring >3 days of IV antibiotics or development of TOA d
Preterm rupture of membranes	N/A	Preterm rupture but not resulting in delivery before 37 weeks gestation	Preterm rupture resulting in delivery before 37 weeks gestation
Preterm contractions /labor/delivery e	Preterm contractions which resolve without medical intervention	Preterm contractions with cervical change which result in medical intervention but not resulting in preterm delivery	Delivery before 37 weeks gestation

Table 8: Solicited Adverse Event Grading Scale (continued)

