**Listing 20: 16.2.11.4: Pregnancy Reports – Still Birth Outcomes**

Subject ID	Date of Initial Report	Fetus Number	Pregnancy Outcome (for this Fetus)	Fetal Distress During Labor and Delivery?	Delivery Method	Gestational Age at Still Birth	Size for Gestational Age	Cord pH	Congenital Anomalies?	Autopsy Performed?	If Autopsy, Etiology for Still Birth Identified?

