**Listing 21: 16.2.11.5: Pregnancy Reports – Spontaneous, Elective, or Therapeutic Abortion Outcomes**

Subject ID	Date of Initial Report	Fetus Number	Pregnancy Outcome (for this Fetus)	Gestational Age at Termination	Abnormality in Product of Conception?	Reason for Therapeutic Abortion

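### SAP Table 75 pools elective abortions with stillbirths in one row, so no pregnancy-outcome summary table gives a separate stillbirth rate and confidence interval by arm

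*SAP*

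**What the plan says.** The Table 75 shell has three rows: live births, spontaneous abortions, and "Elective Abortions or Still Births". Each carries n, % and a 95% CI for BOOSTRIX, Td and all subjects. The denominator is given in the footnote: "Note: N= Number of subjects in the Maternal Safety Population". The text of SAP 9.5 describes the same table: "number of live births, and number of spontaneous abortions, elective abortions or still births by treatment group will be presented". That sentence names elective abortions and stillbirths but does not say clearly whether they share a count.

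The other maternal pregnancy tables (77, 79 and 81) have one row for Pregnancy Loss. SAP Table 8 describes this as a pregnancy not ending in a live birth. Under it are miscarriage in the first or second trimester and "Fetal death at or after 20 weeks of gestation (stillbirth".

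The subject listings keep the outcomes apart. Listing 20 is headed "Pregnancy Reports – Still Birth Outcomes" and Listing 21 is headed "Spontaneous, Elective, or Therapeutic Abortion Outcomes". Neither shell has a treatment-group column.

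**The concern.** An elective abortion is a maternal decision; a stillbirth is a fetal death. A percentage and interval computed on their sum estimate neither. Safety for the fetus is a primary objective (SAP 3.1.1), and the matching endpoint in SAP 3.2.1 asks for description and comparison by arm of pregnancy-specific events in women and their infants. Vaccination falls between 14 0/7 and 26 6/7 weeks, so most of the remaining pregnancy lies beyond 20 weeks, where Table 8 calls a fetal death a stillbirth. A reader would expect the pregnancy-outcome table to show that outcome on its own. With the few events expected, one or two elective terminations could alter how the row compares between arms.

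**Working it through.** The plan states no stillbirth rate and no figure that depends on this row, so there is nothing to reproduce. The check traces each planned display in which a stillbirth could appear.

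1. **Table 75.** Elective abortions and stillbirths share a row. If the row shows k in an arm, the number of stillbirths may be anything from 0 to k.
2. **Tables 77, 79 and 81.** Stillbirth falls within Pregnancy Loss, together with miscarriage.
3. **Tables 78, 80 and 82.** These are infant tables. They have no pregnancy-loss or stillbirth row.
4. **Subtraction.** Taking the spontaneous abortions in Table 75 from Pregnancy Loss in Table 77 gives only an approximation. The two components in Table 8 overlap in the second trimester from 20 weeks on, and the SAP does not say whether an elective abortion counts as pregnancy loss.
5. **Listing 20.** Every stillbirth is listed. The arm comes from the sort order (SAP 9 sorts listings by treatment group) or from linking subject IDs.
6. **Table 61.** A footnote to Table 8 gives stillbirth as an example of an event that meets AE/SAE reporting. Table 61 shows the treatment group for each SAE.
7. **Tables 55 and 56.** These give n, % and 95% CI by preferred term for each arm, including an any-time column. SAP 9.3 says all reported adverse events enter the summaries. However, pregnancy-related events have their own listing (13), apart from unsolicited events (12), and the SAP does not say outright that they also enter Tables 55 and 56. A stillbirth row there is likely but not certain.

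The possible size can be illustrated from the planned arms (SAP 5: "The study is planned to enroll 200 pregnant women (133 BOOSTRIX, 67 Td") and an **assumed** stillbirth risk of 1% to 3%. The multiplier is (67p + 1) / 67p, the effect of one elective termination on the expected pooled count in the Td arm.

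| Assumed risk p | Expected, 133p | Expected, 67p | Td multiplier |
|---|---|---|---|
| 1% | 1.33 | 0.67 | 1.67 / 0.67 = 2.5 |
| 2% | 2.66 | 1.34 | 2.34 / 1.34 = 1.75 |
| 3% | 3.99 | 2.01 | 3.01 / 2.01 = 1.5 |

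In observed counts, one stillbirth among 67 is 1.5% (exact 95% CI 0.04 to 8.0). With one elective termination added, the row reads 2/67 = 3.0% (0.4 to 10.4). These intervals use the Clopper-Pearson method that SAP 9.5 names for Tables 77 and 78; no method is stated for Table 75.

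**The case against.** A reader might infer from Table 75 that stillbirths by arm are never reported, or are reported only in a subject listing. The documents do not support either reading. Listing 20 isolates stillbirths, Table 61 should show each one with its treatment group, and Tables 55 and 56 would probably give n, % and CI by preferred term.

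Fetal loss is also already compared between arms. Table 79 gives Pregnancy Loss with a difference, its interval and a Fisher p-value. The components that Table 8 lists do not include elective abortion, so on that reading the comparison is free of it, although the broader heading leaves some doubt. Table 75 carries no test, so an elective termination in its pooled row changes no p-value in that table.

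SAP 9.5 can be read as an ordinary list of separate counts: "number of spontaneous abortions, elective abortions or still births by treatment group will be presented". On that reading the fault lies in one row label of the shell. Protocol 11.4.2 expects few untoward fetal outcomes and plans to list them, with a Fisher comparison only if more than 5% of women are affected. Nor do the documents give any reason to expect elective terminations in this trial.

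Most of this stands, and it limits the point to presentation. It does not justify the pooled row: the table that summarises pregnancy outcomes would still report a sum with no clear meaning, while the listings already separate its parts.

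**Conclusion.** The point holds as a reporting gap. No pregnancy-outcome summary table gives stillbirths by arm with a rate and interval, and the row nearest to it mixes fetal death with maternal choice. The stillbirth count is recoverable from other displays, so nothing is lost from the record, and no planned test is shown to be affected.

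The size is uncertain. If there are no elective abortions, the pooled count equals the stillbirth count, but Table 75 alone would not tell the reader so. If one occurs in the Td arm, the expected pooled count rises by a factor of 1.5 to 2.5 under an assumed stillbirth risk of 3% down to 1%. A reader who takes only the 2% case might call that a near doubling; the arithmetic gives a 75% rise. The change is worth making because the outcome belongs to a primary safety objective and the correction is almost free.

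**What to change.** - **Table 75:** split the row into stillbirth and elective or therapeutic abortion, each with n, % and an exact 95% CI by arm. Therapeutic abortions are in Listing 21 but have no row in Table 75 now.
- **SAP 9.5:** say explicitly that these outcomes are counted separately.
- **Listings 20 and 21:** add a treatment-group column.
- **Optional:** add a stillbirth row to the Fisher comparison in Table 79. With so few events expected it would add little, and the study is not designed to test a specific null hypothesis.

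The required changes cost one extra table row, one listing column and a clearer sentence. Listings 20 and 21 already hold the data separately, so nothing new is collected.

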**Table 76: Summary of Infant Size for Gestational Age at Birth**

Size	BOOSTRIX (N=X)			Td (N=X)			All Subjects (N=X)		
	n	%	95% CI	n	%	95% CI	n	%	95% CI
Small for Gestational Age	x	xx	x.x, x.x	x	xx	x.x, x.x	x	xx	x.x, x.x
Appropriate for Gestational Age									
Large for Gestational Age									

Note: N= Number of subjects in the Infant Safety Population

**Table 77: Number and Percentage of Maternal Subjects Experiencing Pregnancy-Related Adverse Events with 95% Confidence Intervals by Symptom and Treatment Group**

Symptom	BOOSTRIX (N=X)			Td (N=X)			All Subjects (N=X)		
	n	%	95% CI	n	%	95% CI	n	%	95% CI
Any Maternal Pregnancy Related Symptom	X	XX	X.X, X.X	X	XX	X.X, X.X	X	XX	X.X, X.X
Pregnancy Loss									
Bleeding									
Postpartum Hemorrhage									
Postabortal Endometritis/Salpingitis									
Preterm Rupture of Membranes									
Preterm Contractions/Labor/Delivery									
Poor Fetal Growth									
Hypertension, Preeclampsia/Eclampsia									
Chorioamnionitis									
Postpartum Endometritis									
Gestational Diabetes									
Other Pregnancy Related AE									
Note: N= Number of subjects in the Maternal Safety Population									

**Table 78: Number and Percentage of Infant Subjects Experiencing Infancy-Related Adverse Events with 95% Confidence Intervals by Symptom, and Treatment Group**

Symptom	BOOSTRIX (N=X)			Td (N=X)			All Subjects (N=X)		
	n	%	95% CI	n	%	95% CI	n	%	95% CI
Any Neonatal and Infant Events	x	xx	x.x, x.x	x	xx	x.x, x.x	x	xx	x.x, x.x
Preterm Birth									
Birth Weight									
Neonatal Complications in a Term Infant									
Other AE in Newborn									
Congenital Abnormalities/Birth Defects									

Note: N= Number of subjects in the Infant Safety Population

**Table 79: Comparison of the Proportion of Maternal Subjects Experiencing Pregnancy-Related Adverse Events by Symptom and Treatment Group**

Symptom	Statistic	BOOSTRIX (N=X)	Td (N=X)
Any Maternal Pregnancy Related Symptom	Proportion (95% CI)	x.xx (x.xx, x.xx)	x.xx (x.xx, x.xx)
	Difference (95% CI)	NA	x.xx (x.xx, x.xx)
	p-value*	NA	0.xxx
Pregnancy Loss	Proportion (95% CI)		
	Difference (95% CI)		
	p-value*		
Bleeding	Proportion (95% CI)		
	Difference (95% CI)		
	p-value*		
Postpartum Hemorrhage	Proportion (95% CI)		
	Difference (95% CI)		
	p-value*		
Postabortal endometritis/salpingitis	Proportion (95% CI)		
	Difference (95% CI)		
	p-value*		
Preterm Rupture of Membranes	Proportion (95% CI)		
	Difference (95% CI)		
	p-value*		
Preterm Contractions/Labor/Delivery	Proportion (95% CI)		
	Difference (95% CI)		
	p-value*		
Poor Fetal Growth	Proportion (95% CI)		
	Difference (95% CI)		
	p-value*		
Hypertension, Preeclampsia/eclampsia	Proportion (95% CI)		
	Difference (95% CI)		
	p-value*		
Chorioamnionitis	Proportion (95% CI)		
	Difference (95% CI)		
	p-value*		
Postpartum Endometritis	Proportion (95% CI)		
	Difference (95% CI)		
	p-value*		
Gestational Diabetes	Proportion (95% CI)		

Table 79: Comparison of the Proportion of Maternal Subjects Experiencing Pregnancy-Related Adverse Events by Symptom and Treatment Group (continued)

Symptom	Statistic	BOOSTRIX (N=X)	Td (N=X)
	Difference (95% CI)		
	p-value*		
Other Pregnancy Related AE	Proportion (95% CI)		
	Difference (95% CI)		
	p-value*		

Note: N = Number of subjects in the Maternal Safety Population.  
\*P-value is based on Fisher's exact test.

**Table 80: Comparison of the Proportion of Infant Subjects Experiencing Infancy-Related Adverse Events by Symptom and Treatment Group**

Symptom	Statistic	BOOSTRIX (N=X)	Td (N=X)
Any Neonatal and Infant Event	Proportion (95% CI)	x.xx (x.xx, x.xx)	x.xx (x.xx, x.xx)
	Difference (95% CI)	NA	x.xx (x.xx, x.xx)
	p-value*	NA	0.xxx
Preterm Birth	Proportion (95% CI)		
	Difference (95% CI)		
	p-value*		
Birth Weight	Proportion (95% CI)		
	Difference (95% CI)		
	p-value*		
Neonatal Complications in a Term Infant	Proportion (95% CI)		
	Difference (95% CI)		
	p-value*		
Other AE in Newborn	Proportion (95% CI)		
	Difference (95% CI)		
	p-value*		
Congenital Abnormalities/Birth Defect	Proportion (95% CI)		
	Difference (95% CI)		
	p-value*		

Note: N = Number of subjects in the Infant Safety Population.  
\*P-value is based on Fisher's exact test.

**Table 81: Number and Percentage of Maternal Subjects Experiencing Pregnancy-Related Events by Symptom, Maximum Severity, and Treatment Group**

Symptom	Severity	BOOSTRIX (N=X)			Td (N=X)			All Subjects (N=X)		
		n	%	95% CI	n	%	95% CI	n	%	95% CI
Any Maternal Pregnancy Related Symptom	None	x	xx	x.x, x.x	x	xx	x.x, x.x	x	xx	x.x, x.x
	Mild									
	Moderate									
	Severe									
Pregnancy Loss	None									
	Mild									
	Moderate									
	Severe									
Bleeding	None									
	Mild									
	Moderate									
	Severe									
Postpartum Hemorrhage	None									
	Mild									
	Moderate									
	Severe									
Postabortal endometritis/salpingitis	None									
	Mild									
	Moderate									
	Severe									
Preterm Rupture of Membranes	None									
	Mild									
	Moderate									

Table 81: Number and Percentage of Maternal Subjects Experiencing Pregnancy-Related Events by Symptom, Maximum Severity, and Treatment Group (continued)

Symptom	Severity	BOOSTRIX (N=X)			Td (N=X)			All Subjects (N=X)		
		n	%	95% CI	n	%	95% CI	n	%	95% CI
	Severe									
Preterm Contractions/Labor/Delivery	None									
	Mild									
	Moderate									
	Severe									
Poor Fetal Growth	None									
	Mild									
	Moderate									
	Severe									
Hypertension, Preeclampsia/eclampsia	None									
	Mild									
	Moderate									
	Severe									
Chorioamnionitis	None									
	Mild									
	Moderate									
	Severe									
Postpartum Endometritis	None									
	Mild									
	Moderate									
	Severe									
Gestational Diabetes	None									
	Mild									
	Moderate									

Table 81: Number and Percentage of Maternal Subjects Experiencing Pregnancy-Related Events by Symptom, Maximum Severity, and Treatment Group (continued)

Symptom	Severity	BOOSTRIX (N=X)			Td (N=X)			All Subjects (N=X)		
		n	%	95% CI	n	%	95% CI	n	%	95% CI
	Severe									
Other Pregnancy Related AE	None									
	Mild									
	Moderate									
	Severe									

Note: N = Number of subjects in the Maternal Safety Populations.

**Table 82: Number and Percentage of Infant Subjects Experiencing Infancy-Related Events by Symptom, Maximum Severity, and Treatment Group**

Symptom	Severity	BOOSTRIX (N=X)			Td (N=X)			All Subjects (N=X)		
		n	%	95% CI	n	%	95% CI	n	%	95% CI
Any Neonatal and Infant Events	None	x	xx	x.x, x.x	x	xx	x.x, x.x	x	xx	x.x, x.x
	Mild									
	Moderate									
	Severe									
Preterm Birth	None									
	Mild									
	Moderate									
	Severe									
Birth Weight	None									
	Mild									
	Moderate									
	Severe									
Neonatal Complications in a Term Infant	None									
	Mild									
	Moderate									
	Severe									

Table 82: Number and Percentage of Infant Subjects Experiencing Infancy-Related Events by Symptom, Maximum Severity, and Treatment Group (continued)

Symptom	Severity	BOOSTRIX (N=X)			Td (N=X)			All Subjects (N=X)		
		n	%	95% CI	n	%	95% CI	n	%	95% CI
Other AE in Newborn	None									
	Mild									
	Moderate									
	Severe									
Congenital Abnormalities/Birth Defects	None									
	Mild									
	Moderate									
	Severe									

Note: N = Number of subjects in the Infant Safety Population.

